10.2.5 Definition of “Unanticipated Adverse Device Effect” (UADE)

Any adverse effect on health or safety or any life-threatening problem or death caused by, or associated with, a device, if that effect, problem, or death was not previously

Document	Created by	Date	Page
CIP PRIMA FS-M Rev3	Clinical Affairs	19 June 2019	36 of 49

identified in nature, severity, or degree of incidence in the investigational plan or application (including a supplementary plan or application), or any other unanticipated serious problem associated with a device that relates to the rights, safety, or welfare of subjects.

An Unanticipated Serious Adverse Device Effect (USADE) occurs when an event's nature, incidence, severity or outcome has not been identified in the current version of the risk analysis report.

An anticipated Serious Adverse Device Effect (ASADE) is an effect which by its nature, incidence, severity or outcome has been identified in the risk analysis report.

10.2.6 Definition of “Device deficiency”

Inadequacy of an investigational medical device related to its identity, quality, durability, reliability, safety or performance. This may include malfunctions, use error or inadequacy in the information supplied by the manufacturer.

10.2.7 Definition of “Use error”

Act or omission of an act that results in a different medical device response than intended by the manufacturer or expected by the user.

Use error includes slips, lapses, and mistakes. An unexpected physiological response of the subject does not in itself constitute a use error.

10.2.8 Event severity classification

Mild: Awareness of a sign or symptom that does not interfere with the patient's usual activity or is transient, resolved without treatment and with no sequelae.

Moderate: Interferes with the patient's usual activity and/or requires symptomatic treatment

Severe: Symptom(s) causing severe discomfort and significant impact on the patient's usual activity and requires treatment

10.2.9 Causality relationship

The investigator will assess the causality of all adverse events in relation to the research, i.e., the relationship between the AE/SAE and the investigational treatment or any other study-related procedures.

Document	Created by	Date	Page
CIP PRIMA FS-M Rev3	Clinical Affairs	19 June 2019	37 of 49

Each SAE will be classified according to five different levels of causality:

- 1) **Not related**: relationship to the device or procedures can be excluded when:
 - the event is not a known side effect of the product category the device belongs to or of similar devices and procedures;
 - the event has no temporal relationship with the use of the investigational device or the procedures;
 - the serious event does not follow a known response pattern to the medical device (if the response pattern is previously known) and is biologically implausible;
 - the discontinuation of medical device application or the reduction of the level of activation/exposure - when clinically feasible – and reintroduction of its use (or increase of the level of activation/exposure), do not impact on the serious event;
 - the event involves a body-site or an organ not expected to be affected by the device or procedure;
 - the serious event can be attributed to another cause (e.g. an underlying or concurrent illness/ clinical condition, an effect of another device, drug, treatment or other risk factors);
 - harms to the subject are not clearly due to use error;
 - In order to establish the non-relatedness, not all the criteria listed above might be met at the same time, depending on the type of device/procedures and the serious event.
- 2) **Unlikely**: The relationship with the use of the device seems not relevant and/or the event can be reasonably explained by another cause, but additional information may be obtained.
- 3) **Possible**: The relationship with the use of the investigational device is weak but cannot be ruled out completely. Alternative causes are also possible (e.g. an underlying or concurrent illness/ clinical condition or/and an effect of another device, drug or treatment). Cases where relatedness cannot be assessed or no information has been obtained should also be classified as possible.
- 4) **Probable**: The relationship with the use of the investigational device seems relevant and/or the event cannot reasonably be explained by another cause, but additional information may be obtained.
- 5) **Definite/Causal relationship**: The serious event is associated with the investigational device or with procedures beyond reasonable doubt when:

Document	Created by	Date	Page
CIP PRIMA FS-M Rev3	Clinical Affairs	19 June 2019	38 of 49

- the event is a known side effect of the product category the device belongs to or of similar devices and procedures;
- the event has a temporal relationship with investigational device use/application or procedures;
- the event involves a body-site or organ that
 - the investigational device or procedures are applied to;
 - the investigational device or procedures have an effect on;
- the serious event follows a known response pattern to the medical device (if the response pattern is previously known);
- the discontinuation of medical device application (or reduction of the level of activation/exposure) and reintroduction of its use (or increase of the level of activation/exposure), impact on the serious event (when clinically feasible);
- other possible causes (e.g. an underlying or concurrent illness/ clinical condition or/and an effect of another device, drug or treatment) have been adequately ruled out;
- harm to the subject is due to error in use;
- In order to establish the relatedness, not all the criteria listed above might be met at the same time, depending on the type of device/procedures and the serious event.

10.2.10 **Investigator Reporting Responsibilities**

10.2.10.1. Notification of events to the sponsor

The investigator should report to the sponsor the following events, whether expected or not, in the corresponding sheet of the CRF, with the exception of AEs/SAEs detected before the patients has signed the patient consent form.

- AE
- SAE
- Device Deficiencies that did not but might have led to a SAE if:
 - Suitable action had not been taken or
 - Intervention had not been made or
 - If circumstances had been less fortunate
- New findings/updated in relation to already reported events

If an AE/SAE is present at the beginning of study prior to the subject providing signed consent to participate in the study, only its worsening should be reported.

Document	Created by	Date	Page
CIP PRIMA FS-M Rev3	Clinical Affairs	19 June 2019	39 of 49

The investigator shall notify the sponsor immediately and not later than 24 hours after the investigator has become aware of a SAE or device deficiency that might have led to a SAE.

The investigator must ensure that all additional relevant information that becomes available is also forwarded to the sponsor immediately after the initial notification.

The investigator shall transmit to the sponsor all relevant supporting documents related to the SAE (i.e., copy of laboratory exams, hospitalization reports indicating the SAE) ensuring anonymization of the documents and indicating the identification number of the subject in the trial.

10.2.10.2. How to report

The investigator will report to the sponsor, without unjustified delay, all serious adverse events and device deficiencies that could have led to a serious adverse device effect.

All Serious Adverse Events (SA(D)Es), including all device deficiencies should be reported to the Sponsor within **24 hours** of awareness of an event via the Adverse Event Electronic Case Report Form in the study's electronic database, as that will trigger an immediate e-notification to the Sponsor and MedPass. Additional information can be provided to the Sponsor or MedPass via email, telephone, or fax using the information below.

Pixium Vision

[name]
[contact]
[contact]

MedPass International SAS

[name]
[contact]
[contact]

The investigator will document all AEs on the Adverse Event Form, including (at a minimum) a description of the event, date of onset, severity, relationship to the investigational device and/or procedure, required interventions, duration, and outcome.

The investigator will monitor all AEs until they are resolved, determined to be a chronic condition or the subject is lost to follow-up. The investigator will report all AEs regardless of whether it is anticipated or unanticipated and regardless of classification, seriousness, intensity, outcome or causality.

Document	Created by	Date	Page
CIP PRIMA FS-M Rev3	Clinical Affairs	19 June 2019	40 of 49

The clinical monitor will ensure that all adverse events have been detailed appropriately and fully documented on subject Case Report Forms.

10.2.11 **Reporting to Ethic Committee / Competent Authority**

Depending on the local requirements or following agreement between both parties, the sponsor or the principal investigator will be responsible for performing safety reporting to the Ethics Committee according to the relevant local regulatory requirements.

The sponsor will be responsible for reporting to the National Competent Authority according to national requirements and in line with MEDDEV 2.7/3 and/or MEDDEV 2.12-1, as applicable.

11. Synopsis of Statistical Approaches

11.1. Introduction and Study Populations

Plans for the specification and reporting of data analyses were developed in consideration of ICH guidelines E3 (Structure and Content of Clinical Study Reports, 1995), E9 (Statistical Principles for Clinical Trials, 1998), and other industry, statistical, and regulatory guidance; opinions regarding good clinical and good statistical practice; and where appropriate, substantive clinical experience.

All patients who meet the inclusion and exclusion criteria and receive a retinal implant will be considered part of the primary safety cohort.

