4.4. Risks and Benefits

4.4.1 Procedural Risks

The primary risks are associated with the surgical implantation of the device; these risks are associated with all retinal surgeries. Pixium Vision's PRIMA system and the corresponding surgical method have undergone risk analysis in accordance with EN ISO 14971:2009, IEC 60601-1 3rd, EN 60601-1-6:2010 and EN 62366:2008.

Document	Created by	Date	Page
CIP PRIMA FS-M Rev3	Clinical Affairs	19 June 2019	13 of 49

The following risks to the patient or tier user were identified during the risk analysis, were found to be acceptable and patient consent form as potential risks.

Risks related specifically to the PRIMA System:

- *Accidents due to temporary loss of visual perception*
- *Accidents due to unexpected non-function of the implant,*
- *Allergenic reaction*
- *Complications due to device explantation*
- *Impairment of residual visual function*
- *Damaged retina*
- *Dermal burns*
- *Electrical shocks from mains power supply*
- *Epileptic seizure*
- *Injury due to use of damaged external device or connection to/interfering with other devices*
- *Injury due to contact from external components*
- *Injury due to battery leakage, fire, or explosion*
- *Meaningful reduction of pre-implant visual function*
- *Minor electrical shock*
- *No increase of visual perception*
- *Retinal or Iris damage of a tier user (patient's family, etc.) or intended user due to exposure of infrared light of damaged external components*
- *Severe or non-severe tissue necrosis*
- *Skin burns to the physician, patient and/or tier user*
- *Strangulation with external components or asphyxiation*
- *Treatment delay*

Common risks from sub-retinal surgery:

- *Adverse reactions and risks to general/local anaesthesia*
- *Choroidal damage*
- *Chronic Hypotony leading to choroidal detachment or other complications*
- *Cell proliferation*
- *Corneal ulcer, damage to iris/crystalline lens*
- *Damaged retina*
- *Endophthalmitis*
- *Hanging eye lid/damaged eye muscle/damaged orbita*
- *Hypertony*
- *Infection*

Document	Created by	Date	Page
CIP PRIMA FS-M Rev3	Clinical Affairs	19 June 2019	14 of 49

- *Long term Hypotony*
- *Opaque media after surgery*
- *Peri-procedural problems typical of any major invasive eye operation*
- *Prolonged or aborted surgical procedure*
- *Retina detachment*
- *Severe non-treatable or non-severe retinal detachment*
- *Severe or non-severe intraocular inflammation/irritation*
- *Sympathetic ophthalmia*

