6.1. Specific Statements of Primary and Secondary Endpoints

The primary efficacy endpoint is the assessment of the device performance to demonstrate principal functionality of the PRIMA system. It is assessed by measuring the capability of the patient to perceive light at specific locations. To prove the functionality of the device, patients are tested with the device on and off. At 6 weeks, 3, 6, 12, 18, 24, and 36 months after implantation. In this feasibility study the fundamental function of the PRIMA device will be tested by OCTOPUS visual field measurement.

The visual acuity will be measured with the Landolt test as a secondary endpoint for all subjects once it is approved. The first time this new test is measured depends on the follow-up time point the subject is approaching and will be the earliest after 18 months follow-up. Afterwards the Landolt C test will be measured at 24 and 36m.

The primary safety endpoint of the study will involve an analysis of the incidence, severity and duration of all adverse events at 1 day, 1 week, 1, 1.5, 3, 6, 12, 18, 24, and 36 months. The safety of the implanted device will be assessed in a series of regular ophthalmologic examinations designed to capture any pathological changes in the eye as a result of device implantation.

All adverse events according to section 10 will be recorded. Every adverse event will be identified by a name defined by the investigator (e.g. retinal detachment). During later analyses of the safety the “incidence” of every adverse event will be compared to adverse event rates of other comparable devices which are already on the market for similar indications (e.g. ARGUS II, Second Sight Medical Products, USA). The investigator rates the “severity” of an adverse event by rating it as mild, moderate or severe. He/she also check if the criteria for serious adverse events according to Section 10 are fulfilled. The investigator also rates the likelihood of adverse events being device related or procedure related by choosing the appropriate term defined in Section 10. All adverse events are followed until they are solved or medically stable. Medically stable events are events that are not expected to be completely resolved but reached a status where no further treatment or treatment change will be necessary. The “duration” of an adverse event is defined as the time between date of onset and the date when the event is resolved or medically stable status has been reached.

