6.9. Participating clinical sites

The trial is designed as a multi-centre trial and the sponsor keeps a list of all participating clinical sites. Since the study uses competitive patient recruitment it is possible that all patients are enrolled in one site.

7. Selection and Withdrawal of Patients

Patients will be assessed for inclusion in the study based on the criteria outlined below. If patients meet the inclusion criteria, they will be invited to participate in the study. After signing the Informed Consent, a detailed study ophthalmological exam will occur in order to verify all Inclusion/Exclusion criteria. If any patients fail to meet Inclusion/Exclusion criteria after the complete study pre-surgical ophthalmological exam, he/she will be withdrawn from the study and considered a screening failure. Once patients meet all Inclusion/Exclusion criteria they will be implanted with the device.

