7.3. Criteria and Procedure Specifications for Subject Withdrawal

Patients may withdraw their consent for participation in the investigation at any time.

Patients may also be withdrawn from the study if:

- He or she significantly fails to comply with the study follow-up schedule;
- In the opinion of the treating investigator continuation in the study jeopardizes the subject's health and/or well-being;
- There are significant protocol violations surrounding the patient's original inclusion in the study;
- Either the Sponsor or a governing regulatory authority discontinues the study.

[figure not shown]
8. Treatment Plan and Follow-Up Periods

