10.2. Procedures for Reporting and Recording Adverse Events

Subjects will be carefully monitored during the study for possible Adverse Events (AEs) from the time the subject signs the Patient Informed Consent form to the completion of their participation in the study. Any AE observed will be fully investigated by the Investigator and classified in line with the definitions of the ISO14155:2011, which are shown below.

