11.2. Objectives

The primary objective of this study is to evaluate the safety and performance of the PRIMA System in patients presenting with dry macular degeneration.

Safety evaluations will involve summarizing the incidence, severity and duration of all adverse events. The safety of the implanted device will be assessed in a series of regular ophthalmologic examinations designed to capture any pathological changes in the eye as a result of device implantation.

Performance will be evaluated by OCTOPUS Visual Field measurement.

Document	Created by	Date	Page
CIP PRIMA FS-M Rev3	Clinical Affairs	19 June 2019	41 of 49

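### The primary safety cohort requires both eligibility and a placed implant, which conflicts with an endpoint covering all adverse events and can leave operated patients out of the primary rates

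*Protocol*

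**What the plan says.** Section 11.1, headed as covering the study populations, has one sentence on the safety population: "All patients who meet the inclusion and exclusion criteria and receive a retinal implant will be considered part of the primary safety cohort". No set of all implanted subjects, or of all subjects operated on, is defined elsewhere in the protocol.

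The endpoint is worded more widely. Section 6.1: "The primary safety endpoint of the study will involve an analysis of the incidence, severity and duration of all adverse events". Section 11.2: "Safety evaluations will involve summarizing the incidence, severity and duration of all adverse events". Under section 10.2, events are collected "from the time the subject signs the Patient Informed Consent form to the completion of their participation in the study".

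The protocol foresees both situations that the cohort sentence does not cover. Section 4.4.1 says "The primary risks are associated with the surgical implantation of the device" and lists "Prolonged or aborted surgical procedure" among the risks of sub-retinal surgery. Section 7.3 gives this as a ground for withdrawal: "There are significant protocol violations surrounding the patient's original inclusion in the study".

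The opening of section 7 describes the intended order of events: criteria are checked at the pre-surgical examination, failures leave as screening failures, and "Once patients meet all Inclusion/Exclusion criteria they will be implanted with the device".

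**The concern.** A safety population should follow exposure. Here the exposure that carries most of the stated risk is the operation, yet membership depends on two other things: whether the patient was properly eligible and whether the implant ended up in the eye.

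Both can be settled after the harm has occurred. A complication during surgery may itself be the reason that no implant is placed. Several criteria also need judgement (useful vision in the fellow eye, severe organ disease, unrealistic expectations), and in an open-label trial a breach may be recognised only once the outcome is known.

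At stake are the primary complication rates of a first-in-human trial. Section 6.1 will compare adverse event incidence with rates for marketed devices. Section 11.4.2 uses an interim report on performance and safety to decide on further development and a pivotal trial.

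**Working it through.** The protocol gives no event rate, power or safety threshold, so there is no planned figure to reproduce. The check sets the texts side by side and then sizes the effect by example.

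**Step 1: who is covered.**

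| Patient | Events collected (10.2) | Within all adverse events (6.1, 11.2) | In the cohort as worded (11.1) |
|---|---|---|---|
| Eligible, implanted | yes | yes | yes |
| Implanted, breach found later | yes | yes | no |
| Surgery started, implant not placed | yes | yes | no |

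The last two rows show the conflict.

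**Step 2: how much surgery precedes the implant.** In section 8.1.5, complete vitrectomy is step 4, the subretinal bleb step 7, the retinotomy step 9 and the 2.0 mm incision step 11. The implant enters the eye only at step 16. A patient whose operation stops before then has already had much of the surgery.

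**Step 3: size.** Inputs: at most five implanted (synopsis, 11.3) and up to ten enrolled (synopsis). Assumption: the patient left out is the only one with the event. The rate is x/n. The exact 95% limits (Clopper-Pearson) are the 2.5% quantile of Beta(x, n − x + 1) and the 97.5% quantile of Beta(x + 1, n − x). For x = 0 the lower limit is 0 and the upper is 1 − 0.025^(1/n).

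- *Implanted but ineligible.* All implanted: 1/5 = 20% (0.5% to 71.6%). Cohort as worded: 0/4 = 0% (0% to 60.2%).
- *Aborted surgery alongside five completed ones.* All operated: 1/6 = 16.7% (0.4% to 64.1%). Cohort as worded: 0/5 = 0% (0% to 52.2%).

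The second example takes the cap as counting implanted subjects, as the synopsis does. Section 6.2 speaks of up to five enrolled. If the aborted case used one of five places, the figures would be those of the first example.

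**Step 4: bounds and direction with five implanted.** If the patient left out has the event, the rate falls by x/5 − (x − 1)/4 = (5 − x)/20. This is 20 points at x = 1 and 15 points at x = 2 (40% to 25%). If the patient left out has no event, the rate rises by x/4 − x/5 = x/20, for example from 1/5 = 20% to 1/4 = 25%. The shift is therefore at most 20 points, and its direction depends on who is left out.

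**Step 5: chance of seeing an event at all.** This is 1 − (1 − p)^n for an assumed true rate p.

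| p | n = 4 | n = 5 | n = 6 |
|---|---|---|---|
| 5% | 18.5% | 22.6% | 26.5% |
| 10% | 34.4% | 41.0% | 46.9% |
| 20% | 59.0% | 67.2% | 73.8% |
| 30% | 76.0% | 83.2% | 88.2% |

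Even with equal risk in every patient, each one dropped lowers the chance of seeing a harm.

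**The case against.** The strongest reply is that the sentence includes and does not expressly exclude. It does not say that only these patients count or that anyone is removed. Read with the opening of section 7, meeting the criteria may simply mean having passed screening, which separates implanted subjects from the up to ten enrolled. Section 11 is a synopsis, and a statistical analysis plan, not at hand, may define a wider set. This stands in part: the text does not settle what happens when a breach is found after surgery. But the sentence is the protocol's only population definition, so a reader would apply it as the rule. The screening reading also leaves the aborted operation uncovered, and a wider primary cohort in a later plan would have to depart from the protocol.

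A reader might infer that these harms disappear from the trial's safety evaluation. The documents do not support that. Events are collected from consent and reported whatever their seriousness or causality (10.2, 10.2.10). They are adjudicated by the independent committee if serious or device or procedure related (6.1, 10.1). They also feed the risk analysis that can stop the study (6.6, footnote), and section 6.2 interrupts the study for an unacceptable related event. None of this depends on the cohort in 11.1.

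A reader might also take section 7.3 as deleting ineligible patients from the analysis. It says only that a patient may be withdrawn from participation and is silent on data already collected.

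Finally, the planned analysis is descriptive, no test or threshold turns on 0/4 against 1/5, and no decision rule is given for the comparison with marketed devices. That limits the consequence but does not make the definition right.

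**Conclusion.** The point holds as a defect in the definition of the primary safety population. Section 11.1 is narrower than the endpoint in sections 6.1 and 11.2, and these must be reconciled. Followed as written, it can leave a harmed, operated patient out of the primary rates.

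The size is up to 20 percentage points for one patient with five implanted, or 16.7 points for one aborted operation alongside five completed ones. These figures are illustrations. They assume that the patient left out is the one with the event, and the protocol gives no probability for either situation. A bias in favour of the device is plausible where a surgical complication causes the abort, but it is not certain, since leaving out an unaffected patient raises the rate. The intervals are very wide and overlap heavily. What changes is whether the primary table shows the harm at all, which matters for the comparison with marketed devices and for the interim report.

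**What to change.** Replace the sentence in section 11.1 with: *The primary safety cohort is every subject in whom implantation surgery was started, whether or not the implant was placed and regardless of eligibility deviations.*

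Give eligible implanted subjects as a supportive table, so that the population intended by the present wording is still shown. Add that withdrawal under section 7.3 does not remove a subject's collected data from the safety cohort.

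The cost is two or three sentences in an amendment, with the analysis plan aligned to it. No new data are needed, because events are already collected from consent. Complication rates may look slightly less favourable. If neither situation has occurred, every estimate stays the same.
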